1.2.1.2 Clinical Studies in Adults

MONARCH 1 (NCT02102490) was a single-arm, open-label, multicenter study in women with measurable HR-positive, HER2-negative metastatic breast cancer whose disease progressed during or after endocrine therapy, had received a taxane in any setting, and who received 1 or 2 prior chemotherapy regimens in the metastatic setting [13]. A total of 132 patients received 200 mg abemaciclib orally twice daily on a continuous schedule until development of progressive disease or unmanageable toxicity. The median duration of treatment was 4.5 months. The most common grade 3/4 toxicities with abemaciclib were diarrhea (20% Grade 3), neutropenia (19% Grade 3, 5% Grade 4), nausea (5% Grade 3), infections (5% Grade 3, 2% Grade 4), fatigue (13% Grade 3), anemia (5% Grade 3), thrombocytopenia (4% Grade 3), and decreased appetite (3% Grade 3).

MONARCH 2 (NCT02107703) was a randomized, placebo-controlled, multicenter study in women with HR-positive, HER2-negative metastatic breast cancer in combination with fulvestrant in patients with disease progression following endocrine therapy who had not received chemotherapy in the metastatic setting [14]. A total of 669 patients were randomized to receive abemaciclib or placebo orally twice daily plus intramuscular injection of 500 mg fulvestrant on days 1 and 15 of cycle 1 and then on day 1 of cycle 2 and beyond (28-day cycles). Patients remained on continuous treatment until development of progressive disease or unmanageable toxicity. MONARCH 2 met its primary endpoint with an improvement in PFS (median 16.4 vs. 9.3 months, HR 0.553, p<0.0001). The most common grade 3/4 toxicities with abemaciclib in MONARCH 2 were neutropenia (24% Grade 3, 3% Grade 4) and diarrhea (13% Grade 3), anemia (7% Grade 3, <1% Grade 4), thrombocytopenia (2% Grade 3, 1% Grade 4), infections (5% Grade 3, <1% Grade 4), nausea (3% Grade 3), ALT increase (4% Grade 3, <1% Grade 4) and fatigue (3% Grade 3). Further details about MONARCH 1 and MONARCH 2 are available in the FDA package insert for abemaciclib.

CONFIDENTIAL

This material is the property of the University of Pennsylvania.

1.3 Nivolumab Mechanism of Action

PD-1 is a member of the CD28 family of T-cell co-stimulatory receptors that also includes CD28, CTLA 4, ICOS, and BTLA. PD-1 signaling has been shown to inhibit CD-28-mediated upregulation of IL-2, IL-10, IL-13, interferon- γ (IFN- γ) and Bcl-xL. PD-1 expression also been noted to inhibit T cell activation, and expansion of previously activated cells. Evidence for a negative regulatory role of PD-1 comes from studies of PD-1 deficient mice, which develop a variety of autoimmune phenotypes. These results suggest that PD-1 blockade has the potential to activate anti-self T-cell responses, but these responses are variable and dependent upon various host genetic factors. Thus, PD-1 deficiency or inhibition is not accompanied by a universal loss of tolerance to self-antigens.

In vitro, nivolumab (BMS-936558) binds to PD-1 with high affinity (EC50 0.39-2.62 nM), and inhibits the binding of PD-1 to its ligands PD-L1 and PD-L2 (IC50 + 1 nM). Nivolumab binds specifically to PD-1 and not to related members of the CD28 family such as CD28, ICOS, CTLA-4 and BTLA. Blockade of the PD-1 pathway by nivolumab results in a reproducible enhancement of both proliferation and IFN- γ release in the mixed lymphocyte reaction (MLR). In vivo blockade of PD-1 by a murine analog of nivolumab enhances the anti-tumor immune response and result in tumor rejection in several immunocompetent mouse tumor models (MC38, SA1/N, and PAN02). Clinical efficacy has been demonstrated in a variety of tumor types, and it is currently FDA approved for the treatment of melanoma, non-small cell lung cancer, Hodgkin's lymphoma, renal cell carcinoma, squamous cell carcinoma of the head and neck, urothelial carcinoma, microsatellite instability-high tumors, and hepatocellular carcinoma

1.3.1 Nivolumab In Hepatocellular Carcinoma

Nivolumab was initially tested in hepatocellular carcinoma in the phase I/II Checkmate-040 study [3]. This was an open-label, non-comparative dose escalation and expansion trial. A total of 262 subjects were treated in the two phases of the study. In the dose-escalation portion, the overall response rate was 15%, with a disease control rate of 58% and a median overall survival of 15.0 months. In the dose expansion phase, an objective response rate of 20% was demonstrated, and median survival was not reached in the overall population. Response rates were similar regardless of viral hepatitis status or prior treatment with sorafenib. Toxicity was manageable, with 25% grade 3/4 adverse events, most commonly rash (23%), AST increase (21%), ALT increase (15%), lipase increase (21%), amylase increase (19%), and pruritis (19%). Treatment-related serious adverse events were seen in 6% of patients in the dose-escalation of cohort. Only 20% of subjects had PD-L1 expression of > 1% by IHC, and this did not correlate with response rate. Based on the results of this study, nivolumab received accelerated approval from the FDA for HCC. A phase III trial (Checkmate-459) comparing sorafenib to nivolumab for the initial treatment of advanced HCC is ongoing.

1.4 Dose Rationale

A phase 1b study of abemaciclib 150mg twice daily with the PD-1 inhibitor pembrolizumab 200mg every 3 weeks in women with breast cancer demonstrated tolerability, with no additional toxicity expected from either therapy as single agents [12]. The toxicities of pembrolizumab and nivolumab are expected to be similar in this study population and thus abemaciclib 150mg twice daily is expected to be similarly tolerable. The initial 7-day run-in of abemaciclib prior to starting nivolumab is based on preclinical data showing enhanced synergy compared to concurrent or sequential dosing [9].

The Checkmate-040 study which led to the accelerated approval of nivolumab in HCC used a dose of 240mg every 2 weeks. More recently, the FDA label for nivolumab has added the option of 480mg every 4 weeks for most nivolumab indications, including in hepatocellular carcinoma. The nivolumab doses of 480 mg Q4W was selected for this study based on clinical pharmacokinetic data and modeling showing similar drug exposure and no change in safety compared to dosing every 2 weeks using either weight-based (3mg/kg) or flat dose (240mg) regimens.

CONFIDENTIAL

This material is the property of the University of Pennsylvania.

2 Study Objectives

2.1 Primary Objective

- To determine ORR of abemaciclib plus nivolumab in HCC as measured by RECIST v. 1.1

2.2 Secondary Objectives

- To determine PFS and DOR of abemaciclib plus nivolumab in HCC as measured by both RECIST v 1.1 and iRECIST. To measure ORR by iRECIST. To summarize OS using Kaplan-Meier methods
- To determine toxicity rates by category using CTCAE v. 5.0

[figure not shown]
2.3 Exploratory Objective

- To correlate outcomes with blood and tumor tissue immune markers pre- and post-therapy to explore potential biomarkers of anti-tumor response

3 Investigational Plan

Subjects with advanced hepatocellular carcinoma will be enrolled in this single-arm open-label phase II study. Subjects will receive abemaciclib monotherapy 150mg twice daily for seven days then will initiate nivolumab 480mg IV every 28 days while continuing twice daily abemaciclib. Subjects will continue therapy until progression of disease, unacceptable toxicity, or withdrawal of consent.

Figure 1: Treatment Schema

3.1 Abemaciclib Dose and Schedule

Abemaciclib will be given at a dose of 150mg by mouth twice daily continuously for the duration of trial therapy.

3.1.1 Dose Modifications for Abemaciclib

If a subject experiences any of the following toxicities (grading per CTCAE v. 5.0) that are considered at least possibly related to abemaciclib, abemaciclib will be modified as follows:

Table 1: Dose Levels for Abemaciclib

Dose Level	Dose of abemaciclib
0	150mg twice daily
-1	100mg twice daily
-2	50mg twice daily
If further dose-reduction beyond 50mg twice daily is required, discontinue abemaciclib permanently	

Hematologic toxicities

- Grade 1 or 2: No abemaciclib dosage adjustment necessary

CONFIDENTIAL

This material is the property of the University of Pennsylvania.

- Grade 3: Withhold abemaciclib until toxicity resolves to \leq Grade 2; no dose reduction of abemaciclib is necessary
- Grade 4 or recurrent Grade 3: Withhold abemaciclib until toxicity resolves to \leq Grade 2 and then resume abemaciclib at the next lower dose (see **Table 1**)

If blood cell growth factors (e.g. filgrastim) are administered, hold abemaciclib for at least 48 hours after the last dose of blood cell growth factor and until toxicity resolves to \leq grade 2. Resume at next lower dose (see **Table 1**) unless already performed for the toxicity that led to the use of the growth factor.

Non-hematologic toxicities:

- Diarrhea: At the first sign of loose stools, begin management with antidiarrheal agents and increase oral fluid intake. Response should be assessed within 24 hours.
 - Grade 1: No abemaciclib dosage adjustment necessary
 - Grade 2: If toxicity does not resolve to \leq Grade 1 within 24 hours, withhold abemaciclib until resolution (no abemaciclib dosage reduction is necessary)
 - Grade 2 that persists or recurs after resumption at the same dose (despite maximal supportive measures): Withhold abemaciclib until toxicity resolves to \leq Grade 1 and then resume abemaciclib at the next lower dose (see **Table 1**)
 - Grade 3 or 4 or requires hospitalization: Withhold abemaciclib until toxicity resolves to \leq Grade 1 and then resume abemaciclib at the next lower dose (see **Table 1**)
- Hepatotoxicity:

Table 2: Dose Modifications and Management Of Abemaciclib For Hepatotoxicity

Monitor ALT prior to the start of abemaciclib therapy, every 2 weeks for the first 2 months, monthly for the next 2 months, and as clinically indicated.

CTCAE Grade	Abemaciclib Dose Modifications
Grade 1 ($>\text{ULN}-3.0 \times \text{ULN}$) Grade 2 ($>3.0-5.0 \times \text{ULN}$)	No dose modification is required.
Persistent or Recurrent Grade 2, or Grade 3 ($>5.0-20.0 \times \text{ULN}$) that does not resolve with maximal supportive measures within 7 days to baseline or Grade 1	Suspend dose until toxicity resolves to baseline or Grade 1. Resume at next lower dose.
Grade 3 ($>5.0 \times \text{ULN}$) with total bilirubin $>2 \times \text{ULN}$, in the absence of cholestasis	Discontinue abemaciclib.
Grade 4 ($>20.0 \times \text{ULN}$)	Discontinue abemaciclib.

To ensure patient safety the investigator should collect specific recommended clinical information and follow-up laboratory tests as shown below in Table 3.

Details for hepatic monitoring depend upon the severity and persistence of observed laboratory test abnormalities. If a study patient experiences elevated ALT $5 \times \text{ULN}$ and elevated TBL $2 \times \text{ULN}$, or ALT $8 \times \text{ULN}$, liver tests, including ALT, AST, TBL, direct bilirubin, gamma-glutamyl transferase (GGT), and creatine phosphokinase (CPK), should be repeated within 3 to 5 days to confirm the abnormality and to

CONFIDENTIAL

This material is the property of the University of Pennsylvania.

determine if it is increasing or decreasing. If the abnormality persists or worsens, clinical and laboratory monitoring should be initiated by the investigator, based on the hepatic monitoring tests below.

In the event that hepatotoxicity requiring discontinuation of abemaciclib is observed, a complete laboratory evaluation as detailed in **Table 3** should be performed.

Table 3: Hepatic Monitoring Tests for a Hepatic Treatment Emergent Abnormality.

Hepatic Hematology	Haptoglobin
Hemoglobin	
Hematocrit	Hepatic Coagulation
RBC	Prothrombin Time
WBC	Prothrombin Time, INR
Neutrophils, segmented and bands	
Lymphocytes	Hepatic Serologies^a
Monocytes	Hepatitis A antibody, total
Eosinophils	Hepatitis A antibody, IgM
Basophils	Hepatitis B surface antigen
Platelets	Hepatitis B surface antibody
	Hepatitis B Core antibody
Hepatic Chemistry	Hepatitis C antibody
Total bilirubin	Hepatitis E antibody, IgG
Direct bilirubin	Hepatitis E antibody, IgM
Alkaline phosphatase	
ALT	Anti-nuclear antibody
AST	Anti-actin antibody
GGT	Anti-smooth muscle antibody
CPK	

Abbreviations: ALT = alanine aminotransferase; AST = aspartate aminotransferase; CPK = creatine phosphokinase; GGT = gamma-glutamyl transferase; Ig = immunoglobulin; INR = international normalized ratio; RBC = red blood cells; WBC = white blood cells.

^a Reflex/confirmation dependent on regulatory requirements and/or testing availability.

Table 4: Dose Modification and Management — Hematologic Toxicities

Monitor complete blood counts prior to the start of abemaciclib therapy, every 2 weeks for the first 2 months, monthly for the next 2 months, and as clinically indicated.	
CTCAE Grade	Abemaciclib Dose Modifications
Grade 1 or 2	No dose modification is required.
Grade 3	Suspend dose until toxicity resolves to \leq Grade 2. Dose reduction is not required.
Grade 3, recurrent, or Grade 4	Suspend dose until toxicity resolves to \leq Grade 2. Resume at next lower dose.
Patient requires administration of a blood cell growth factor	Suspend abemaciclib dose for at least 48 hours after the last dose of blood cell growth factor and until toxicity resolves to \leq Grade 2.

CONFIDENTIAL

This material is the property of the University of Pennsylvania.

	Resume abemaciclib at next lower dose unless the dose was already reduced for the toxicity that led to the use of the growth factor.
--	--

General Guidance for Interstitial lung disease (ILD)/Pneumonitis events

Interstitial lung disease (ILD) / pneumonitis has been identified as an adverse drug reaction for abemaciclib. Adverse events reported included events such as interstitial lung disease, pneumonitis, obliterative bronchiolitis, organizing pneumonia, pulmonary fibrosis. The majority of events were Grade 1 or Grade 2 with serious cases and fatal events reported.

Monitor for clinical symptoms or radiological changes indicative of ILD/pneumonitis and please ask patients to report any new or worsening pulmonary symptoms. Symptoms may include hypoxia, cough, dyspnea, or interstitial infiltrates on radiologic exams.; these symptoms should be investigated and treated as per local clinical practice and/or guidelines (including corticosteroids as appropriate). Infectious, neoplastic, and other causes for such symptoms should be excluded by means of appropriate investigations. Investigations may include imaging such as high resolution computer tomography (HRCT), bronchoalveolar lavage (BAL), and biopsy as clinically indicated (see also Table 7: *refer to dose adjustment table for interstitial lung disease/pneumonitis*).

Table 5: Dose Modification and Management — Interstitial Lung Disease/Pneumonitis

CTCAE Grade	Abemaciclib Dose Modifications
Grade 1 or 2	No dose modification is required.
Persistent or recurrent Grade 2 toxicity that does not resolve with maximal supportive measures within 7 days to baseline or Grade 1	Suspend dose until toxicity resolves to baseline or Grade 1. Resume at next lower dose.
Grade 3 or 4	Discontinue abemaciclib.

Table 6: Dose Modification and Management — Nonhematologic Toxicities Excluding Diarrhea, ALT Increased, and ILD/Pneumonitis

CTCAE Grade	Abemaciclib Dose Modifications
Grade 1 or 2	No dose modification is required.
Persistent or recurrent Grade 2 toxicity that does not resolve with maximal supportive measures within 7 days to baseline or Grade 1	Suspend dose until toxicity resolves to baseline or Grade 1. Resume at next lower dose.
Grade 3 or 4	

- Other toxicities attributable to abemaciclib:
 - Grade 1 or 2: No dose modification is required
 - Persistent or recurrent Grade 2 toxicity that does not resolve with maximal supportive measures within 7 days to baseline or Grade 1: Withhold abemaciclib until toxicity resolves to baseline or \leq Grade 1. Resume at next lower dose (see **Table 1**).

CONFIDENTIAL

This material is the property of the University of Pennsylvania.

- Grade 3 or 4: Withhold abemaciclib until toxicity resolves to baseline or \leq Grade 1. Resume at next lower dose (see **Table 1**).

For any toxicity of abemaciclib (regardless of grade) that, despite optimal supportive care, is felt by the treating Investigator to present a risk to safety of the study subject, additional dose reduction, treatment delay, or treatment discontinuation is permitted at the discretion of the treating Investigator. Subjects in whom abemaciclib is held or discontinued may continue to receive nivolumab and remain on study.

3.1.2 General Guidance for Increases in Serum Creatinine and Assessment of Renal Insufficiency with Abemaciclib

Elevation of serum creatinine is observed with abemaciclib and is due to a pharmacological inhibitory effect of abemaciclib on renal tubular transporters without affecting glomerular function. The rise in serum creatinine (mean increase, 0.2 mg/dL) occurs within the first 28-day cycle of abemaciclib, and remains elevated but stable throughout the treatment period, and is reversible upon treatment discontinuation. Alternative markers (such as BUN, cystatin C level, or cystatin C calculated GFR) which are not based on creatinine, may be considered to determine whether renal function is impaired.

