3.2 Nivolumab Dose and Schedule

Nivolumab will be administered at a dose of 480mg IV every 28 days. Treatment with nivolumab will begin after an initial 7-day treatment period with abemaciclib monotherapy (see Figure 1: Treatment Schema). No dose modifications of nivolumab are permitted. Subjects who experience toxicity related to nivolumab will be managed in accordance with guidelines in the management algorithms provided in the nivolumab package label, with modifications relevant to the treatment population

Table 4: Dose Modifications and Delays For Nivolumab Toxicity

Adverse Reaction	Severity	Dose Modificaiton
Colitis	Grade 2 diarrhea or colitis	Withhold dose
	Grade 3 diarrhea or colitis	Withhold dose
	Grade 4 diarrhea or colitis	Permanently discontinue
Pneumonitis	Grade 2 pneumonitis	Withhold dose
	Grade 3 pneumonitis	Permanently discontinue
Hepatitis	
• If AST/ALT is within normal limits at baseline and increases to more than 3 and up to 5 times the ULN• If AST/ALT is more than 1 and up to 3 times ULN at baseline and increases to more than 5 and up to 20 times the ULN	Withhold dose
	If AST or ALT increases to more than 20 times the ULN or total bilirubin increases to more than 3 times the ULN	Permanently discontinue
Hypophysitis	Grade 2 or 3 hypophysitis	Withhold dose
	Grade 4 hypophysitis	Permanently discontinue
Adrenal Insufficiency	Grade 2	Withhold dose
	Grade 3 or 4	Permanently discontinue
Type 1 Diabetes Mellitus	Grade 3 hyperglycemia	Withhold dose

CONFIDENTIAL

This material is the property of the University of Pennsylvania.

	Grade 4 hyperglycemia	Permanently discontinue
Nephritis	Serum creatinine more than 1.5 and up to 6 times the ULN	Withhold dose
	Serum creatinine more than 6 times the ULN	Permanently discontinue
Skin	Grade 3 rash or suspected Stevens-Johnson syndrome (SJS) or toxic epidermal necrolysis (TEN)	Withhold dose
	Grade 4 rash or confirmed SJS or TEN	Permanently discontinue
Encephalitis	New-onset moderate or severe neurologic signs or symptoms	Withhold dose
	Immune-mediated encephalitis	Permanently discontinue
Other	Other Grade 3 Adverse Reaction (except for amylase or lipase elevations in absence of clinical pancreatitis)	
 Withhold dose for first occurrence Permanently discontinue for recurrence of same Grade 3 adverse event
	Life-threatening or Grade 4 adverse reaction	Permanently discontinue
	Grade 3 myocarditis	Permanently discontinue

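### Table 2 is ambiguous on Grade 3 ALT: by word order, a first related event outside the discontinuation row need not be held for up to 7 days

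*Combined protocol and SAP*

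**What the plan says.** Section 3.1.1 applies to toxicities judged at least possibly related to abemaciclib. Table 2 covers ALT in four rows.

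- Grade 1 and Grade 2 (up to 5 x ULN): no change.
- "Persistent or Recurrent Grade 2, or Grade 3 ($>5.0-20.0 \times \text{ULN}$) that does not resolve with maximal supportive measures within 7 days", where resolution means a return to the baseline level or to Grade 1. The action is a hold until that point, then a restart one dose level lower.
- Grade 3 with total bilirubin above 2 x ULN and no cholestasis: discontinue.
- Grade 4: discontinue.

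The text below Table 2 asks for repeat liver tests in 3 to 5 days when ALT is 8 x ULN, or 5 x ULN with bilirubin 2 x ULN. It also recommends the Table 3 follow-up tests, without timing. It gives no dosing instruction.

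Tables 5 (ILD/pneumonitis) and 6 (other non-hematologic toxicities) use nearly the same condition for Grade 2 alone: "Persistent or recurrent Grade 2 toxicity that does not resolve with maximal supportive measures within 7 days to baseline or Grade 1". Each gives Grade 3 or 4 its own row. The title of Table 6 excludes ALT increases.

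**The concern.** The 7-day condition directly follows the Grade 3 term. Whether it governs Grade 3 alone or both grades, suspension for a first Grade 3 ALT waits until 7 days have passed without resolution. An immediate hold follows only if the reader skips the adjacent term and ties the condition back to Grade 2.

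Two investigators can therefore apply the row differently to the same value: one holds at once, the other continues at full dose for a week. The row governs liver toxicity in subjects with HCC, who may enter with a Child-Pugh score up to 7 and ALT up to 3 x ULN (section 4.1). They also receive nivolumab, which has its own hepatitis rules. Section 1.2.1.1 names hepatic metabolism as the main clearance route of abemaciclib.

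**Working it through.** The plan states no figure on this point, so the check is mainly a comparison of rules.

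**Step 1. What the protocol requires for a first related Grade 3 event**

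| Toxicity | Rule | Wait? |
|---|---|---|
| Hematologic, 3.1.1 bullets and hematologic table | "Suspend dose until toxicity resolves to \leq Grade 2. Dose reduction is not required" | No |
| Diarrhea, 3.1.1 | "Grade 3 or 4 or requires hospitalization: Withhold abemaciclib until toxicity resolves to" Grade 1 or less | No |
| ILD/pneumonitis, Table 5 | Discontinue | No |
| Other, bullets below Table 6 | "Grade 3 or 4: Withhold abemaciclib until toxicity resolves to baseline or" Grade 1 or less | No |
| ALT with bilirubin above 2 x ULN, no cholestasis, Table 2 | Discontinue | No |
| Any other Grade 3 ALT, Table 2 | Suspend | 7 days by word order |

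The action cell for Grade 3 or 4 in Table 6 is blank in the text available here. The bullet below that table states the hold, so the comparison rests on the bullet.

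Nivolumab makes a further contrast (section 3.2). The hepatitis row "If AST/ALT is more than 1 and up to 3 times ULN at baseline and increases to more than 5 and up to 20" times ULN leads to a withheld dose with no waiting period. If one ALT rise is judged related to both drugs, nivolumab stops at once while abemaciclib may continue.

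**Step 2. Does another rule fill the 7 days?**

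- The no-change row of Table 2 ends at Grade 2.
- The discontinuation rows need bilirubin above 2 x ULN without cholestasis, or Grade 4.
- Table 6 excludes ALT, and the bullets below it cover only other toxicities.
- The 3-to-5-day repeat orders tests, not a hold.
- The nivolumab rule governs nivolumab only.

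On the word-order reading, no row applies until day 7. If the event resolves before then, no row ever applies.

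**Step 3. Would non-resolution at day 7 be seen?**

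At ALT 8 x ULN, or 5 x with bilirubin 2 x, the 3-to-5-day repeat falls inside the window. For ALT above 5 and below 8 x ULN with lower bilirubin, no timed repeat is tied to day 7. Scheduled chemistries can be 14 days apart (cycle 1 day 15 to day 29, section 6), although Table 2 also allows ALT checks as clinically indicated.

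**Step 4. Size**

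- Doses in 7 days: 2 per day x 7 = 14; 14 x 150 mg = 2100 mg. A hold at the first value gives 0.
- Rise needed for a subject entering at the ALT limit, by the ULN multiples of Table 2: 5 / 3 = 1.67-fold.
- Frequency: section 1.2.1.2 gives 4% Grade 3 ALT with abemaciclib plus fulvestrant in breast cancer. Assuming that this rate carries over:
  - expected cases: 27 x 0.04 = 1.08
  - P(0) = 0.96^27 = 0.332, so P(at least 1) = 0.668
  - P(exactly 1) = 27 x 0.04 x 0.96^26 = 0.374
  - P(2 or more) = 1 - 0.332 - 0.374 = 0.294

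These figures count all Grade 3 ALT at the assumed rate. Those meeting the discontinuation row are not affected.

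**The case against.** The best counter-argument is that the row already means an immediate hold. It opens with the same reference to persistent or recurrent Grade 2 as Tables 5 and 6, where the 7-day condition belongs to Grade 2 alone. Read that way, every ALT grade in Table 2 has an action; read by word order, Grade 3 has a gap until day 7. This stands as evidence of intent and is why a drafting slip is the likely explanation. It does not change the word order that an investigator would be applying.

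There are also safeguards. The treating investigator may delay treatment for any toxicity thought to put the subject at risk (section 3.1.1). The Medical Monitor is consulted as needed on dose modifications (section 11.1). Higher ALT values prompt a repeat within 3 to 5 days. All of this stands and lowers the practical risk, particularly as subjects are enrolled at two locations of one institution. None of it requires a hold.

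A reader might infer that the protocol sets the most lenient rule for the liver overall. The documents do not support that. Grade 3 ALT with raised bilirubin and no cholestasis is discontinued, and so is Grade 4 ALT, whereas Grade 3 or 4 blood counts, diarrhea and other toxicities allow resumption. The leniency is confined to Grade 3 ALT outside the discontinuation row.

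**Conclusion.** The point holds as an ambiguity in an operative dosing rule. By word order, a first related Grade 3 ALT outside the discontinuation row has no required hold for up to 7 days and needs no action if it resolves in that time. After 7 days without resolution, suspension is mandatory. The documents give no reason for a wait, and the sister tables suggest that none was meant.

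Two stronger inferences should be avoided. One is that the plan deliberately continues abemaciclib through Grade 3 ALT; the parallel wording in Tables 5 and 6 argues against this. The other is that at most one subject is affected. The figure of about 1 in 27 is an expected value, with roughly a 29% chance of two or more at the same rate. That rate comes from breast cancer with fulvestrant and no PD-1 inhibitor; the rate for this combination in HCC is not given. The 14 doses assume that nobody uses the discretionary hold and that day-7 status is actually checked, so they are illustrative and not a firm ceiling.

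The change is worth making because it costs little and concerns liver safety. Confidence is medium because the sentence can be read both ways.

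**What to change.** Split the suspend row of Table 2 in two and leave both discontinuation rows unchanged.

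1. Persistent or recurrent Grade 2 ALT that has not returned to baseline or Grade 1 after 7 days of maximal supportive care: suspend until baseline or Grade 1, then resume at the next lower dose.
2. Any Grade 3 ALT (above 5 and up to 20 x ULN) that does not meet the discontinuation row, including cases with bilirubin above 2 x ULN and cholestasis: suspend at the first value until baseline or Grade 1, then resume at the next lower dose.

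The second row should be defined by not meeting the discontinuation row, and not by bilirubin alone. A row limited to bilirubin at or below 2 x ULN would leave cholestatic cases with no instruction; at present they fall in the suspend row.

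The cost is one table row, with no added visits or tests. The downside is some earlier holds and dose reductions in subjects whose Grade 3 ALT would have settled within 7 days. With about 1 of 27 subjects expected to have Grade 3 ALT at the assumed 4% rate, few such cases are likely, but that number is not an upper limit.
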